## **7.2 Decimal Precision Convention:**

The minimum and maximum statistics will be presented to the same number of decimal places as the original data. The mean and median, Confidence Intervals (CI) will be presented to one more decimal place than the original data, whereas the SD and Standard Error (SE) will be presented to two more decimal places than the original data. P-value will be presented with three decimal places. If p-value is closer to 0, then it should be reported as “<0.001” and if it is closer to 1, then it should be reported as “>0.999”.

## **8. HANDLING OF MISSING DATA**

No imputation of missing data will be done.

To handle missing or partial AE and concomitant medication dates, the following rules will be applied.

### **8.1 For Partial Start Dates:**

1. If the year is unknown, then do not impute the date but assign a missing value.
2. If the month is unknown, then:
  - i. If the year matches the year of the first dose date, then impute the month of the dose date.
  - ii. Otherwise, assign “January.”
3. If the day is unknown, then:
  - i. If the month and year match the month and year of the first dose date, then impute the day of the dose date.
  - ii. Otherwise, assign “01.”

### **8.2 For Partial End Dates:**

1. If the year is unknown, then do not impute the date but assign a missing value.
2. If the month is unknown, then assign “December.”
3. If the day is unknown, then assign the last day of the month.

After implementing the rules above, to determine whether AEs (or medications) with missing start or stop dates are pre-treatment or on/after treatment, the following strategy will be used:

1. If both start date and stop date are missing, then the most conservative approach is taken, and the AE (or medication) is considered to be treatment emergent (or concomitant medication).
2. If the start date is missing but the stop date is not missing and is on or after the day of study dose administration, then the most conservative approach is taken, and the AE (or medication) is considered to be treatment emergent (or concomitant medication).

3. If the start date is missing but the stop date is not missing and is before the day of study dose and after the date of signed informed consent, then the AE (or medication) is considered to be before treatment (or prior medication).
4. If the start date is not missing but the stop date is missing, then the most conservative approach is taken, and medication is considered to be concomitant while the AE is defined by start date.

## 9. DEFINITIONS

**Baseline:** Baseline is defined as the last non-missing value prior to the first administration of the study drug, unless otherwise stated.

**Change from Baseline:** The change from baseline values will be calculated as post-baseline value (p) minus the baseline value (b).

**Percent (%) Change from Baseline:** The % change from baseline values will be calculated as  $(p - b)/b \times 100$ .

**Adverse Event (AE):** Any untoward medical occurrence associated with the use of an Investigational Product (IP) in humans, whether considered related to the IP and does not imply any judgment about causality. The Investigator will assess each AE for seriousness as defined in the protocol and severity and causality based on their best medical judgment, the observed symptoms associated with the event, and the available information on the Investigational Product (IP) as defined in the protocol. The relatedness guidance provided below can be used to assist in determining the relationship of the IP to the AE.

- **Not Related:** Based upon available information regarding subject history, disease process, relationship of adverse event to dosing and drug pharmacology, there is no reasonable relationship between the IP and the adverse event.
- **Possibly Related:** Relationship exists between the adverse event and IP, when the adverse event follows a reasonable sequence from the time of the IP administration, but could also have been produced by the subject's clinical state or by other drugs administered to the patient.
- **Probably Related:** Relationship exists between the adverse event and the IP when the adverse event follows a reasonable sequence from the time of IP administration, follows a known response pattern of the drug class, is confirmed by improvement on stopping the IP and the IP is the most likely of all causes.
- **Definitely Related:** Relationship exists between the adverse event and the IP when the adverse event follows a reasonable sequence from the time of the IP administration, follows a known response pattern of the drug class, is confirmed by improvement on stopping the IP and no other reasonable cause exists.

**Treatment-emergent Adverse Events (TEAEs):** A treatment-emergent adverse event (TEAE) is any new AE that emerges on or after the start of the first study drug administration having been

absent in pre-treatment (or) worsen in severity relative to the pre-treatment state following administration of study drug.

**Composite Congestion Score:** A composite congestion score (CCS) will be calculated by summing the individual scores for orthopnoea, JVD, and pedal oedema.

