6.2.2. Treatment Phase (Day 0)

After the screening activities have been completed and laboratory analyses reviewed to confirm eligibility, the patient may be randomized (2:1) to receive either Furoscix or continued medical therapy with oral diuretics. Subjects randomized to continued medical therapy will follow the same schedule of assessments, excluding study product administration.

The initial dose of the study product should be administered after randomization. If randomized to Furoscix, product training with subject and/or caregiver will be conducted. The initial dose of the study product may be administered in the clinic or at home on the day of enrollment. Study staff will dispense additional doses of Furoscix. Subjects will be provided a Subject Diary in which to record any observed device issues and self-assessments that will be completed at home.

The Subject will be reminded to use the provided equipment to weigh themselves and record their blood pressure and heart rate and complete the patient global assessment VAS upon returning home and first thing in the morning on Day 1. They will also be reminded to bring their study product (device) and Subject Diary back to the clinic on Day 1.

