### **4. SAMPLE SIZE**

Fifty-one (51) subjects will be included and randomly assigned in a 2 to 1 ratio to receive Furoscix (n=34) or continued medical therapy (n=17) in the home setting with 30 days of follow-up. Given the exploratory nature of this study, no formal power analysis of sample size was conducted.

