### **15.3 Analysis of Safety**

Descriptive statistics and appropriate tests will be used to summarize and compare the safety parameters between treatment groups. All safety analyses will be performed on the safety population. Treatment group comparisons may assess the significance of the difference between treatment and control groups.

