#### **15.3.1 Adverse Events**

Adverse events will be mapped to the Medical Dictionary for Regulatory Activities (MedDRA™) dictionary, version 23.1 . Adverse events (AE) will be summarized using number and percentage of subjects within each category of each variable overall for any AE, TEAE, serious AE, treatment related AE, AE resulting in death, AE leading to treatment discontinuation, and AE leading to study discontinuation. The incidence rates of AE will also be presented for severity, outcome, causality, and seriousness. For subjects with more than one AE within a given variable (e.g., severity), the event with the highest level of severity, outcome or causality, seriousness, respectively, will be reported. Incidence rates will also be presented for the System Organ Class (SOC) and Preferred Term (PT) of each AE. Data presented will include the number of subjects and percentage of subjects, the SOC and PT for each AE. All AEs will be presented in a listing for the Safety Population.

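### The SAP defines treatment-emergent events by a first dose that controls never receive, so no control event with a known start date can qualify, and the date and medication rules share the gap.

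*SAP*

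**What the plan says.** SAP 9 has two routes to a TEAE. The event is either "any new AE that emerges on or after the start of the first study drug administration", or it meets the second limb, which reads "absent in pre-treatment (or) worsen in severity relative to the pre-treatment state following administration of study drug". Both routes need a dose of study drug.

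Protocol 6.2.2 says of the control arm: "Subjects randomized to continued medical therapy will follow the same schedule of assessments, excluding study product administration". SAP 4 puts 17 of the 51 subjects in that arm.

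TEAEs appear in two outputs. The AE overview in SAP 15.3.1 summarises subjects "overall for any AE, TEAE, serious AE, treatment related AE, AE resulting in death", among other categories, and SAP 15.3.2 lists TEAEs sorted by treatment group. On inference, SAP 15.3 says: "Treatment group comparisons may assess the significance of the difference between treatment and control groups".

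Three other rules use the dose as their reference:
- SAP 8.1 on an unknown start day: "If the month and year match the month and year of the first dose date, then impute the day of the dose date"; failing that, the first of the month. An unknown month is handled the same way, with January as the fallback.
- SAP 8.2, items 2 and 3 of the classification strategy, compare a stop date with the day of study dosing.
- SAP 15.3.8 separates prior from concomitant medication by the start of study treatment.

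**The concern.** Adverse events are assessed from screening on Day 0 (Protocol 6.2.1), before any treatment. The TEAE row is therefore the one meant to separate events arising on study treatment from those already present. In a randomized comparison that separation needs a time point that exists in both arms, and here it exists in one.

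A programmer who follows the SAP cannot produce a meaningful control figure for this row. One who does not follow it must invent a reference time, in an open-label study, after the plan is fixed. The purpose of the trial is pilot effectiveness and safety data for a pivotal trial. A TEAE row with events on Furoscix and none on control, or with no control column, could be carried forward as a safety signal that the event rule created.

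**Working it through.** **Arm sizes.** 51 × 2/3 = 34 and 51 × 1/3 = 17, matching SAP 4. The SAP adds that "no formal power analysis of sample size was conducted", so there is no planned safety precision to reproduce.

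**Applying the rules to a control subject.**
1. Start date known: SAP 9 compares it with a first administration that does not exist. Neither limb can be met, so the event is not a TEAE.
2. Start date partial, year known: SAP 8.1 has no dose month or day to match, so only the fallbacks apply (January, or the first of the month). The completed date again has nothing to be compared with.
3. Start date missing, stop date present: items 2 and 3 of SAP 8.2 need a dose day and cannot be evaluated.
4. Both dates missing: item 1 of SAP 8.2 makes the event treatment-emergent with no dosing condition. This is the only way a control event can qualify.
5. Medications: SAP 15.3.8 cannot classify a control's medication that has a stop date. SAP 8.2 gives a default (concomitant) when the stop date is missing and the start date is known, or when both are missing.

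**Which table results.** SAP 14 requires at least one dose for the Safety population, and all safety analyses use that population. Read literally, controls have no denominator. If they are admitted, as a comparison with control requires, they score 0/17 apart from case 4.

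**Illustration of size, controls admitted and scored 0/17.** The documents give no AE rate, so a common true rate r in both arms is assumed. The test is a two-sided Fisher exact test at 0.05.
- 7/34 against 0/17 gives p = 0.080; 8/34 gives p = 0.040. Eight Furoscix subjects with a TEAE are enough.
- Chance of nominal significance = Σ over x ≥ 8 of Binomial(x; 34, r).
- With both arms scored, the chance is the sum of Binomial(a; 34, r) × Binomial(b; 17, r) over all pairs with Fisher p < 0.05.

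| r | Expected, Furoscix (34r) | Expected, control (17r) | Chance of a true 0/17, (1−r)^17 | p < 0.05, controls at 0/17 | p < 0.05, both arms scored |
|---|---|---|---|---|---|
| 10% | 3.4 | 1.7 | 0.167 | 1.7% | 2.4% |
| 20% | 6.8 | 3.4 | 0.023 | 36.7% | 3.3% |
| 30% | 10.2 | 5.1 | 0.002 | 84.4% | 3.2% |
| 40% | 13.6 | 6.8 | 0.0002 | 98.6% | 3.4% |

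At 10% there is no inflation, because eight events are rarely reached.

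**Partial start dates.** SAP 8.1 was applied to every Day 0 in a 365-day year and every true onset from Day 0 to Day 30, weighted equally (an assumption), with and without a dose date.
- Day unknown: Furoscix events are never dated before Day 0; control events are in 47.5% of cases. In the other 52.5% both arms receive the same date.
- Month and day unknown: 0% against 95.6%.
- Neither arm's date is ever moved later than the true onset.

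These shares take effect only if a Day 0 cut is applied to controls. They show that changing SAP 9 alone, with SAP 8.1 left as it is, would leave a difference between arms.

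**The case against.** The strongest reply is that this is a narrow wording gap. Much of it stands:
- A reader might infer that the SAP will print 34 Furoscix subjects against a structural zero of 17. It will not: under SAP 14 controls are absent. The 0/17 figure needs controls admitted first, and even then a control event with both dates missing counts.
- A reader might infer that the primary safety endpoint is biased. SAP 10.1 names AEs, AESIs and SAEs, not TEAEs, and those incidences do not use the SAP 9 rule. The any-AE figure sits in the same overview. Who enters the Safety population is a separate matter.
- A reader might infer that partial dates are pushed in opposite directions by arm. Both arms' start dates move earlier or stay put, and the end-date rules are identical. Only status relative to Day 0 differs, and only when onset shares the Day 0 month (or year, if the month is unknown). Nor does this add to the TEAE bias, since a control count already at zero cannot fall.
- A reader might take the false-positive rates as properties of the plan. SAP 15.3 only permits between-arm tests, none is specified for TEAEs, and the rates are assumed. Partial onset dates should also be few, given daily contact to Day 7, diaries, and the onset date required in SAE reports.

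What the reply does not supply is a reference time for controls. The nearest candidate, in SAP 15.2, concerns efficacy baselines and itself refers to device start. Correcting the Safety population alone would not help, because the event rule would still exclude every dated control event.

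**Conclusion.** The point holds as a defect in the event rule. It follows from the text alone and needs no assumed figure: no control AE with a known start date can be treatment-emergent, for 17 of 51 subjects (33%). The TEAE row and listing by arm therefore cannot support a comparison. The same anchor leaves control partial start dates with only the fallback branches, leaves items 2 and 3 of SAP 8.2 unevaluable for controls, and leaves their prior/concomitant status under SAP 15.3.8 undefined.

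Its reach stops there: all-AE, SAE and AESI incidence does not depend on the TEAE definition. The 37%, 84% and 99% figures are illustrative. They rest on equal assumed rates, on controls being admitted but scored 0/17, and on a Fisher test the SAP does not specify.

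**What to change.** In SAP 8.1, 8.2, 9 and 15.3.8, replace the first dose with the randomization date and time (Day 0) as the reference in both arms. Make all four changes together, and alongside them admit controls to the safety set in SAP 14. A TEAE is then an event that starts, or worsens, on or after randomization. Keep onset after the first infusion as a descriptive flag for the Furoscix arm only. Do not add a new end to the TEAE window; nothing in this point calls for one.

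The cost is SAP wording and one derivation. Every subject is randomized on Day 0 and first dosing is planned for the same day, so no new data collection is foreseen. If only the randomization date is held, the SAP should state how events on Day 0 are ordered. The small downside is that events between randomization and the first infusion count as emergent in the Furoscix arm; the flag identifies them.

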## 10. ENDPOINTS

### 10.1 Primary Endpoints

- Improvement in a composite/combined morbidity/mortality endpoint at 30 days using the Finkelstein Schoenfeld method.
  - CV death
  - HF hospitalization
  - Urgent ED/Clinic visit for worsening heart failure (defined as IV diuretics, augmentation of or new administration of metolazone)
  - Percent change in NT-proBNP from baseline at Day 7
- Incidence of Adverse Events, Adverse Events of Special Interest, and Serious Adverse Events

### 10.2 Secondary Endpoints (through 30 days)

- Days alive and HF event free days
- Global Visual Analog Scale
- Composite Congestion Score (CCS)
- 5-point Current Dyspnea Score
- 7-point Dyspnea Score
- Health-related quality of life (KCCQ-12)
- Renal Function and Electrolytes
- Weight
- Exercise tolerance (6MWT)
- Percent Lung Fluid Measurement via Remote Dielectric Sensing (ReDS)

### 10.3 Adverse Events of Special Interest over 30 Days

- Worsening kidney function, defined as increase of  $\geq 0.5$  mg/dL in serum creatinine
- Hyperkalemia, defined as  $K > 5.5$  mEq/L
- Hypokalemia, defined as  $K < 3.5$  mEq/L
- Hypomagnesemia, defined as  $Mg < 1.5$  mg/dL

## 13. INTERIM ANALYSIS

There will be no formal interim analysis.

## 14. ANALYSIS POPULATIONS

**Intent-to-Treat (ITT):** ITT population will include all randomized subjects. The subjects in ITT population will be analyzed according to the treatment group they were originally randomized.

**Safety:** Safety population will include all randomized subjects who received at least one dose of Investigational Product (IP). The subjects in the Safety population will be analyzed and presented according to the actual treatment received.

**Per-Protocol (PP):** All randomized subjects who received at least one dose of the IP, completed the 30 Day clinic visit assessments and have a Day 7 NT-proBNP value available for analysis.

All effectiveness analyses, including the primary endpoint and baseline characteristics will be performed on the ITT and Per-Protocol populations. Safety analyses will be performed on the safety population.

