| INVESTIGATIONAL PRODUCT | Furosemide Injection, 80 mg per 10 mL for subcutaneous administration via the Infusor (Furoscix On-body Infusor (hereinafter referred to as Furoscix Infusor)) |
| STUDY OBJECTIVES | 
Primary Objective:
 
 Provide pilot data on effectiveness and safety to inform a pivotal trial 
Secondary Objectives:
 
 Inform population enrichment strategies Refine pivotal trial endpoints and analytical methods Identify operational challenges of study design Assess patient adherence, competence, and experience Familiarize staff and patients with device application and use |
| ENDPOINTS | 
Primary Endpoints:
 
 Improvement in a composite/combined morbidity/mortality endpoint at 30 days using the Finkelstein Schoenfeld method. 
 Cardiovascular (CV) death Heart Failure (HF) hospitalization Urgent Emergency Department (ED)/Clinic visit for worsening heart failure (defined as Intravenous (IV) diuretics, augmentation of or new administration of metolazone) Change in NT-proBNP from baseline at Day 7 Incidence of Adverse Events, Adverse Events of Special Interest, and Serious Adverse Events 
Secondary Endpoints (through 30 days):
 
 Days alive and HF event free days Global Visual Analog Scale Composite Congestion Score (CCS) 5-point Current Dyspnea Score 7-point Dyspnea Score Health-related quality of life (Kansas City Cardiomyopathy Questionnaire (KCCQ-12)) Renal Function and Electrolytes Weight Exercise tolerance (Six Minute Walking Test (6MWT)) % Lung Fluid Measurement via Remote Dielectric Sensing (ReDS) |

| | |
|------------------------------------|---|
| STUDY DURATION | 9 months |
| PARTICIPANT DURATION | 30 days |

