8.2. Analysis Populations

- Intent-to-Treat (ITT): All randomized subjects.
- Safety: All randomized subjects who received at least one dose of the Investigational Product.
- Per-Protocol (PP): All randomized subjects who received at least one dose of the Investigational Product AND completed the Day 30 clinic visit assessments AND have a Day 7 NT-proBNP value available for analysis.

All effectiveness analyses, including the primary endpoint and baseline characteristics will be performed on the ITT and Per-Protocol populations as further defined in the SAP. Safety analyses will be performed on the safety population.

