8.6. Safety Analyses

Safety analysis will be performed on the safety population. No imputation will be performed for missing data. The incidence (number and percentage of subjects) of adverse events will be presented overall and by MedDRA System Organ Class (SOC) and Preferred Term (PT) for each treatment group. This analysis will be repeated for serious adverse events, for treatment-related adverse events, adverse events of special interest and for adverse events leading to premature study withdrawal.

Descriptive statistics at each time point will be presented for laboratory variables, vital signs, and body weight, stratified by treatment group.

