### 15.2.1 Primary Efficacy Analysis

The primary efficacy endpoint is the improvement in a composite/combined morbidity/mortality endpoint at 30 days using the Finkelstein Schoenfeld method. The analysis of the primary efficacy endpoint will be conducted for the ITT and PP populations. Each component of the primary endpoint will be compared in pairwise fashion hierarchically. Each patient is compared to all other patients with respect to each of the following endpoints hierarchically. The algorithm is as follows when doing a pairwise comparison of Patient B to Patient A:

- CV death at 30 days:
  - if Patient A survives to 30 days and patient B dies before 30 days, then score = -1 for Patient B
  - if Patient B survives to 30 days and patient A dies before 30 days, then score = +1 for Patient B
  - if both patients survive or if both die , then move to the comparison on the next component.
- HF hospitalization at 30 days:
  - if Patient A is not hospitalized for worsening heart failure (WHF) and patient B is, then score = -1 for Patient B
  - if Patient A is hospitalized for WHF and patient B is not, then score = +1 for Patient B
  - if both patients are not hospitalized or if both are hospitalized, then move to the comparison on the next component.
- Urgent ED/Clinic visit at 30 days for WHF (defined as IV diuretics, augmentation of or new administration of metolazone)
  - if Patient A does not have an Urgent/ED visit for WHF and patient B does have a visit, then score = -1 for Patient B
  - if Patient A does have an Urgent/ED visit for WHF and patient B does not have a visit, then score = +1 for Patient B
  - if both patients have an Urgent/ED visit for WHF, then move to the comparison on the next component.

- if both patients do not have an Urgent/ED visit for WHF, then move to the comparison on the next component.
- Percent Change in NT-proBNP from baseline at 7 days (without imputation):
  - if Patient A's change from baseline at 7 days in NT-proBNP < Patient B's change from baseline at 7 days in NT-proBNP, then score = -1 for Patient B
  - if Patient A's change from baseline at 7 days in NT-proBNP > Patient B's change from baseline at 7 days in NT-proBNP, then score = +1 for Patient B
  - If tied, score=0 for Patient B.

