#### Concomitant Medications

Concomitant medications are defined as prescribed medications and therapies, and over the counter (OTC) preparations, including herbal preparations and vitamins, other than Study medication taken during the study i.e., Concomitant medications are medications taken by subject on/after the start of first study-drug administration. If a medication starts before study entry and continues through the study that will be considered both as prior and concomitant.

Prior and concomitant medication will be categorized by preferred Term and ATC level X class per World Health Organization Drug Dictionary (WHODRUG; Version Global C3 2021SEP) and will be summarized by treatment group and overall, for the Safety Population. The count and percentage of patients using each medication will be displayed. Patients who taken the same medication (in terms of PT) more than once will be counted only once for that medication.

All Prior and concomitant medications will be presented in a listing for the Safety Population.

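### Safety and Per-Protocol both require a dose of Furoscix, which controls never receive, so as written each holds 0 of 17 controls; ITT is unaffected

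*SAP*

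**What the plan says.** **Populations.** SAP Section 14: "Safety population will include all randomized subjects who received at least one dose of Investigational Product (IP". Subjects in that set are then grouped by the treatment they actually took. Protocol 8.2 sets the same condition for Safety and defines PP as "All randomized subjects who received at least one dose of the Investigational Product AND completed the Day 30 clinic visit assessments", with an available Day 7 NT-proBNP value as a further condition. SAP 14 repeats the PP definition. Neither document gives an alternative route into either set for controls.

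**Who gets the product.** The Protocol synopsis names the investigational product as "Furosemide Injection, 80 mg per 10 mL for subcutaneous administration via the Infusor", and Protocol 5.2 names no other. For the control arm, Protocol 6.2.2 says: "Subjects randomized to continued medical therapy will follow the same schedule of assessments, excluding study product administration". No crossover to Furoscix is provided for.

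**What is to be reported on these sets.**
- Protocol 8.6: the incidence "of adverse events will be presented overall and by MedDRA System Organ Class (SOC) and Preferred Term (PT) for each treatment group", repeated for SAEs and AEs of special interest. SAP 15.3 confines all safety analyses to the Safety set and foresees treatment-versus-control comparisons.
- SAP 15.3.8: prior and concomitant medications, diuretics included, "will be summarized by treatment group and overall, for the Safety Population".
- SAP 15.2.1: "The analysis of the primary efficacy endpoint will be conducted for the ITT and PP populations". SAP 15.2.1.1, 15.2.2 and 15.4 also require PP versions of the component, secondary and subgroup analyses.

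**Dating rules.** SAP 9 defines a treatment-emergent AE as "any new AE that emerges on or after the start of the first study drug administration", or one that worsens after it. The partial-start-date rules (SAP 8.1) and the prior/concomitant split (SAP 15.3.8) also refer to first dosing.

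**The concern.** The entry condition for two of the three analysis sets can be met in one arm only, yet the plan asks for by-arm or between-arm results on both.

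The safety side matters most. The incidence of AEs, AEs of special interest and SAEs is listed among the primary endpoints, and the trial's primary objective is pilot effectiveness and safety data to inform a pivotal trial. Run as written, those tables have a Furoscix column and nothing beside it, and the SAP plans no ITT version as a fallback. The medication summary, which would show what diuretics the comparator arm took, omits the comparator arm as well.

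On the effectiveness side, the PP repeat of the primary analysis cannot be run. A programmer would have to improvise a rule for controls, and different programmers could choose differently: all randomized controls, or only those followed up, with treatment-emergent status counted from one date or another. In an open-label trial such choices should not be left until data are in hand.

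**Working it through.** **1. Arm sizes.** The SAP (Sections 2 and 4) gives 51 subjects randomized 2:1. 51 × 2/3 = 34 and 51 × 1/3 = 17, which reproduces its stated 34 and 17.

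**2. Membership under the definitions as written.**

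| Set | Dose of product required? | Furoscix (max) | Control |
|---|---|---|---|
| ITT | No | 34 | 17 |
| Safety | Yes | 34 | 0 |
| PP | Yes, plus Day 30 assessments and Day 7 NT-proBNP | 34 | 0 |

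The share excluded by wording is 17/51 = 33%.

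**3. Could a dosing error supply a comparator?** If k controls received Furoscix by mistake, Safety would show them by treatment taken: 34 + k under Furoscix and still 0 under control. In PP at most k such subjects could count as controls, and only if PP is grouped by randomized arm, which the SAP does not state.

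**4. The Finkelstein-Schoenfeld test on PP.** SAP 15.2.1 gives T = Σ D_i U_i / √[ n1·n2 / (n(n−1)) · Σ U_i² ]. Put in n1 = 34, n2 = 0, n = 34:
- Numerator: every D_i = 1, so it is the sum of all U_i. Each pairwise score of +1 for one patient is −1 for the other, so the sum is 0.
- Denominator: √[ 34·0 / (34·33) · Σ U_i² ] = 0.
- T = 0/0, undefined.

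With n1 = 34 and n2 = 17 the factor n1·n2 is positive. Arbitrary simulated values gave a numerator of −52 and a denominator of about 100.1, so the ITT test can be computed. Those values show only that the test can be calculated.

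**5. PP analyses left without a second group.**
- Finkelstein-Schoenfeld: Day 7, Day 3, and excluding baseline NT-proBNP below 125 pg/mL = 3
- Components (SAP 15.2.1.1) = 4
- Secondary comparisons (SAP 15.2.2) = 10
- Subgroup interactions (SAP 15.4) = 12
- Total 3 + 4 + 10 + 12 = 29

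This is a minimum, because the between-group baseline comparisons on PP are not counted. All 29 have ITT counterparts.

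**6. Safety outputs that lose the control column.** These are the AE, AESI and SAE incidence tables (SAP 15.3.1 to 15.3.3), laboratory and physical-examination shifts (15.3.4, 15.3.5), prior and concomitant medications (15.3.8), and medical history (15.1).

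**7. Precision once corrected (context only).** The documents give no AE rate, so a common incidence p is assumed. The 95% half-width for a 34 versus 17 difference is 1.96·√[p(1−p)(1/34 + 1/17)]:
- p = 0.10: 0.175
- p = 0.30: 0.267
- p = 0.50: 0.291

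These figures describe the corrected comparison, not the defect. At p = 0.10 the control arm expects only 1.7 events, so the normal approximation is rough there. As written, no difference can be estimated at all.

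**The case against.** The strongest reply is that this is a drafting slip with obvious intent. Grouping Safety by treatment taken would be redundant if everyone in it took Furoscix, SAP 15.3 speaks of treatment and control groups, and the trial is an exploratory pilot whose ITT primary test is intact. The intent is indeed apparent, but it supplies no rule. Grouping by treatment taken assigns a column to subjects already in the set; it does not admit an undosed subject. The amendment log also records that the dose condition was added to the Safety definition in Amendment 5, so it is not leftover text.

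Several narrower points deserve weight:
- *Important safety information survives on ITT.* This is correct. CV death, HF hospitalization and urgent visits keep by-arm ITT analyses with confidence intervals, as does serum creatinine, and vital signs are summarized by arm on ITT. The AE, AESI and SAE tables do not. The mock tables cited in SAP 7.1 are not available to check, but SAP 14 and 15.3 point to Safety only.
- *Control AEs have a collection window.* This is also correct. Protocol 6.2.1 and Section 7 assess AEs from screening in both arms. The dating gap concerns treatment-emergent status, partial start dates and the prior/concomitant split.
- *Medication status has other anchors.* SAP 15.3.8 does mention study entry and use during the study, but its operative clauses tie the split to first dosing, so the ambiguity remains for controls.
- *Baseline has the same flaw.* SAP 9 does anchor baseline to first dosing, but SAP 15.2 sets it at Day 0 for all analyses, which is workable for controls.
- *Different reference times by arm create different windows.* They do, but the first dose is due on the day of randomization, so the difference is at most hours on Day 0.

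**Conclusion.** The concern holds and must be corrected before analysis. A stated rule gives a wrong result: Safety and PP each contain at most 34 Furoscix subjects and 0 of 17 controls. The primary safety endpoint cannot be reported by arm, and at least 29 planned PP analyses, including the repeat of the primary test, have no comparator. ITT membership and ITT analyses are unaffected, and control AEs and medications are still collected.

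The conclusion rests on two readings of the text: that the investigational product means Furoscix alone, and that controls receive none, as planned. Accidental dosing of a control would not restore a control column in Safety. The only assumed figures are the AE rates behind the half-widths, and the conclusion does not depend on them.

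**What to change.** Limit the dose condition to the Furoscix arm in both SAP 14 and Protocol 8.2:

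- **Safety:** randomized subjects with at least one Furoscix dose, plus subjects randomized to continued medical therapy with at least one clinic or phone contact after randomization; grouping by treatment taken stays as it is. The contact requirement is one reasonable choice. The sponsor may prefer another, but it must be written down.
- **PP:** at least one Furoscix dose in the Furoscix arm, or randomization to continued medical therapy in the control arm. The Day 30 assessment and Day 7 NT-proBNP conditions stay the same in both arms. State whether PP is grouped by randomized or actual treatment.
- **Reference date for controls:** use randomization for treatment-emergent status (SAP 9), partial start dates (SAP 8.1) and the prior/concomitant split (SAP 15.3.8). The date is enough if the time is not recorded.
- **Protocol 7.7.4:** its documentation requirement covers events after dosing of study product; reconcile this with Section 7 and 6.2.1, under which AEs are assessed from screening in both arms.

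The cost is a wording change in the SAP and protocol. No new visits, data or subjects are needed, because control AEs, medications and the randomization date are already collected.
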